16.1.1. ALL AEs

AEs will be presented by SOC, High Level Term (HLT), and PT for AE incidence and number of events for DB period, OL extension period. These will be presented by frequency and dose at onset. Listings

Document:

\

Author:

Version Number:
Version Date:Final 1.0
24FEB2020Template No: CS_TP_BS016 Revision 4
Effective Date: 01Apr2016

Reference: CS_WI_BS005

for each subject will be included. A listing of all AEs will be presented for DB period, OL extension period.

AEs will also be presented by maximum severity and by strongest relationship to the study medication as specified in the sections below for DB period, OL extension period.

AEs that occurred in $\geq 5\%$ of subjects in either treatment group will be summarized by SOC and PT for DB period, OL extension period.

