Subjects randomized to SEP-363856 will receive flexible doses of SEP-363856 (25, 50, or 75 mg/day). Subjects will receive SEP-363856 25 mg/day for 1 week (Days 1 - 7). If there are no safety or tolerability issues, subjects should be up-titrated to 50 mg/day at Visit 4 (Week 2). Subjects still receiving SEP-363856 25 mg/day must have their dose up-titrated to 50 mg/day at Visit 5 (Week 3), unless approved to stay at 25 mg/day by the Medical Monitor due to safety and tolerability concerns. At the investigator's discretion, subject may up-titrate to 75 mg during scheduled visits. During the double-blind period up-titration will not be allowed after Visit 6 (Week 5). Dose reductions to 50 mg/day or 25 mg/day will be allowed by 1 dose level, at any

time for reasons of safety and tolerability. During the double-blind period, following a dose reduction, subjects may increase their dose to the next dose level up to Visit 6 (Week 5) at the Investigator's discretion and only during scheduled visits. If safety or tolerability issues result in study medication dose discontinuation or reduction, the Investigator must contact the Medical Monitor before the subject is rechallenged. The study medication can be re-introduced if agreed to by the Investigator and Medical Monitor.

Figure 2: Dosing Schematic

Notes:

- Dose reduction is allowed at any time for reasons of safety or tolerability; during unscheduled or scheduled visits.
- During the Double-Blind Period, up-titration to a prior dose level is allowed at Investigator's discretion and only during a scheduled visit.
- At Visit 5 (Week 3), the dose should be up titrated to 50mg/day. In the event of tolerability/safety concerns, the dose may remain at 25 mg/day with Medical Monitor approval.
- Visit 6 (Week 5) is the last visit where up-titration can occur during the Double-Blind Period.

Open-label Extension Period:

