6.7. TREATMENT GROUPS

There are several doses administrated in this flexibly-doses study but statistical analysis will describe/analyze Placebo group versus SEP-363856 all doses pooled. Apart from some exposure tables, no analysis will be performed by doses received.

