13. STUDY MEDICATION EXPOSURE

Duration of exposure to study medication will be summarized for the safety population.

Interruptions, compliance, and dose changes are not taken into account for duration of exposure.

Duration (in days) of exposure will be summarized both as a continuous variable for double-blind treatment period and open-label extension period, and categorically:

For double-blind:

Document:

\

Author:

Version Number:
Version Date:

Final 1.0
24FEB2020

Template No: CS_TP_BS016 Revision 4
Effective Date: 01Apr2016

Reference: CS_WI_BS005

- Number and percentage of subjects with drug exposure ≥ 1 , ≥ 4 , ≥ 7 , ≥ 14 , ≥ 21 , ≥ 28 , ≥ 35 , and ≥ 42 days;
- Number and percentage of subjects with drug exposure for 1 - 3, 4 - 6, 7 - 13, 14 - 20, 21 - 27, 28 - 34, 35 - 41 and ≥ 42 days.

For open-label:

- Number and percentage of subjects with open-label extension study drug exposure ≥ 1 , ≥ 7 , ≥ 14 , ≥ 21 , ≥ 28 , ≥ 56 , and ≥ 84 days;
- Number and percentage of subjects with extension study drug exposure for 1 - 6, 7 - 13, 14 - 20, 21 - 27, 28 - 55, 56 - 83 and ≥ 84 days.

The modal daily dose during the double-blind period and the open-label period (i.e. the dose level that a subject was on for the most number of days during the study) will be summarized categorically by treatment group:

- o 25 mg/day
- o 50 mg/day
- o 75 mg/day
- o Tie between 25 mg/day and 50 mg/day
- o Tie between 25mg/day and 75 mg/day
- o Tie between 50mg/day and 75 mg/day
- o Tie between 25mg/day, 50 mg/day, and 75 mg/day

Include histogram showing distribution of each dose by visit. Include linear plots for each subject showing dose taken over time.

For DB period, the number of days that a subject was on the 25 mg/day dose level, on the 50 mg/day dose level and on the 75 mg/day dose level will also be summarized, both as a continuous variable and categorically:

- o 1 - 3 days
- o 4 - 6 days
- o 7 - 13 days
- o 14 - 20 days
- o 21 - 27 days
- o 28 - 34 days
- o 35 - 41 days
- o ≥ 42 days

For OL period, the number of days that a subject was on the 25 mg/day dose level, on the 50 mg/day dose level and on the 75 mg/day dose level will also be summarized, both as a continuous variable and categorically:

- o 1 - 6 days
- o 7 - 13 days
- o 14 - 20 days

Document:

\

Author:

Version Number:

Final 1.0

Version Date:

24FEB2020

Template No: CS_TP_BS016 Revision 4
Effective Date: 01Apr2016

Reference: CS_WI_BS005

- 21 – 27 days
- 28 – 55 days
- 56 – 83 days

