An overall summary of the incidence of adverse events for DB period, OL extension period within each of the categories described in the following sections will be provided as specified in the templates. This summary for DB period will also be repeated by the race, sex, age, number of prior hospitalizations for PDP, and duration of PDP subgroups. The overall incidence summary for DB period, OL extension period and overall period will also be provided for AEs related to study medication.

Listings for DB period, OL extension period will be provided for all AEs, AEs leading to discontinuation of study medication, AEs leading to discontinuation from the study, serious adverse events (SAE), and AEs leading to death. A listing for pre-treatment events will also be presented.

For incidence summaries, each subject will be counted only once within each SOC and PT. If not otherwise specified, all summaries will present incidence (number of subjects and percentages) and number of events.

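### AEs by dose at onset are to be shown as counts and percentages with no stated denominator per dose and no account of time at each dose, so under flexible titration the columns mix risk with duration

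*SAP*

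**What the plan says.** SAP 16.1.1 tabulates all AEs by system organ class, high level term and preferred term (PT) for the double-blind and open-label periods, and adds: "These will be presented by frequency and dose at onset". The default statistic is in SAP 16.1: "If not otherwise specified, all summaries will present incidence (number of subjects and percentages) and number of events". The counting rule there is: "For incidence summaries, each subject will be counted only once within each SOC and PT". SAP 16.1.2 and 16.1.3 add the dose at the time of discontinuation.

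SAP 6.7, on treatment groups, says: "Apart from some exposure tables, no analysis will be performed by doses received".

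SAP 13 does derive time at each level. One sentence begins "For DB period, the number of days that a subject was on the 25 mg/day dose level" and goes on to 50 and 75 mg, and the open-label period is handled the same way. Nothing links these variables to the AE tables.

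Protocol 7.1 has active subjects take 25 mg on Days 1 to 7, with a step to 50 mg expected at Visit 4 if tolerated. Then: "Subjects still receiving SEP-363856 25 mg/day must have their dose up-titrated to 50 mg/day at Visit 5 (Week 3), unless approved to stay" at 25 mg by the Medical Monitor. The next step is optional: "At the investigator's discretion, subject may up-titrate to 75 mg during scheduled visits". In the double-blind period no increase is allowed after Visit 6, and reductions are allowed at any time.

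**The concern.** A table with columns for 25, 50 and 75 mg invites a comparison across columns. Because subjects move through the doses in sequence and stay at each for different lengths of time, a longer stay collects more onsets even if the daily risk is the same. A reader could take the excess at 50 mg as a dose effect when it is largely a matter of days observed.

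This matters because protocol 7.3.2 says the drug has not been given before in Parkinson's disease or its psychosis, and the sample size section gives exploring the tolerability of flexible dosing as part of the purpose. The planned exposure-response work in SAP 17.2 concerns the SAPS-PD score, not AEs. SAP 6.7, read literally, also excludes the table that SAP 16.1.1 asks for.

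**Working it through.** The documents state no figure for AEs by dose, so there is none to reproduce.

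**Inputs from the documents.** Visits 4, 5 and 6 fall on Days 8, 15 and 29 (protocol Table 2). Double-blind dosing ends on Day 42, since the Day 43 visit is the day after the last dose (footnote a to the schedule). About 24 subjects are on active drug (SAP 3.4).

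**Assumption.** The AE onset rate is not in the documents. I take a constant rate h, equal at every dose: 0.01 per day, with a range of 0.005 to 0.03.

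**Step 1: scheduled days at 25/50/75 mg.**
- 50 mg at Visit 4, then unchanged: 7/35/0
- 50 mg at Visit 4, 75 mg at Visit 5: 7/7/28
- 50 mg at Visit 4, 75 mg at Visit 6: 7/21/14
- 50 mg at Visit 5, 75 mg at Visit 6: 14/14/14

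**Step 2: the planned statistics on the 7/35/0 path.** Expected onsets = 24 × h × days. At h = 0.01 this gives 24 × 0.01 × 7 = 1.68 at 25 mg and 24 × 0.01 × 35 = 8.40 at 50 mg, a ratio of 1:5. The chance of at least one onset at a level = 1 − exp(−h × days):

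| h per day | 25 mg | 50 mg |
|---|---|---|
| 0.005 | 3.4% | 16.1% |
| 0.01 | 6.8% | 29.5% |
| 0.02 | 13.1% | 50.3% |
| 0.03 | 18.9% | 65.0% |

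For the two columns to match on this path, the daily risk at 25 mg would have to be 5 times that at 50 mg. In the open-label period, a subject who goes to 50 mg at Visit 8 and stays has 7 and 77 days, giving 6.8% and 53.7% at h = 0.01.

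**Step 3: a path without distortion.** On 14/14/14 every level shows 13.1% at h = 0.01.

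**Step 4: a mixed arm.** Put 8 subjects on each of 7/35/0, 7/7/28 and 7/21/14, with h = 0.01.

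| | 25 mg | 50 mg | 75 mg |
|---|---|---|---|
| Subjects ever at level | 24 | 24 | 16 |
| Subject-days | 168 | 504 | 336 |
| Expected onsets | 1.68 | 5.04 | 3.36 |
| % with onset, denominator 24 | 6.8 | 18.4 | 12.5 |
| % with onset, denominator ever at level | 6.8 | 18.4 | 18.7 |
| Onsets per 100 subject-days | 1.0 | 1.0 | 1.0 |

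The 75 mg percentage depends on the denominator, which the SAP does not state. Under either choice the percentages follow time at dose. Only the last row recovers the equal risk that was put in.

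**The case against.** The strongest reply is that this is one descriptive table. SAP 16 plans no treatment-group comparisons for safety unless specified, and the safety objectives treat 25, 50 or 75 mg as one flexible regimen. Exposure by dose will be reported alongside (SAP 13), and the format of the tables sits in templates that are not among the documents. All of that stands, and it keeps the priority low. It does not remove the problem: overall days at dose would let a reader work out only a crude total rate, not one per AE term.

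Four stronger readings are tempting and are not supported.

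- *The table can rank the doses in either direction.* Suppose n subjects reach 75 mg on Day 15, with a first-onset risk of 1% per day. Onsets at 75 mg are then n × 0.99^14 × (1 − 0.99^28), or 5.11, 2.56 and 1.28 for n = 24, 12 and 6. Divided by 24 these are 21.3%, 10.7% and 5.3%, so 75 mg could look worst or safest. Divided by subjects ever at 75 mg they are 21.3% each time. The reversal needs the arm size as denominator, and the SAP does not say that.
- *The table shows days and not risk.* It shows the product. Doubling the daily risk at 25 mg moves that column from 6.8% to 13.1%.
- *Titration is forced.* Only the step to 50 mg is close to that, and it has a Medical Monitor exception. The step to 75 mg is discretionary.
- *A recurring event is credited to one dose only, in the only look at tolerability by dose.* The counting rule does not say whether it applies within or across dose columns, and event counts are also required. SAP 16.1.2 and 16.1.3 report dose at discontinuation, and SAP 13 plans a shift table of dose-adjustment decisions.

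It is also fair to say that SAP 16.1.1's word for frequency is ambiguous: it could mean table order, counts, or the once/intermittent/continuous item in protocol 12.3. Reading it as counts and percentages rests on the SAP 16.1 default.

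**Conclusion.** The point holds in a limited form. As written, the dose-at-onset columns reflect risk multiplied by time at dose. On the 7/35-day path the distortion is 1:5 in expected onsets whatever the rate, and 6.8% against 29.5% of subjects at an assumed 1% per day. It vanishes when time is equal across doses. These sizes rest on a constant rate that is the same at every dose, on visits at their nominal days, and on no dose reductions. The missing denominator is a separate gap that affects mainly the 75 mg column. SAP 6.7 and SAP 16.1.1 contradict each other as worded and must be reconciled.

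Rates per subject-day would remove the duration effect only. Dose stays confounded with time since first dose, because 25 mg always comes first, and with tolerability, because subjects with AEs may be held or reduced. No primary, secondary or inferential result is affected. This is a cheap improvement of low priority.

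**What to change.** In SAP 16.1.1, for the SEP-363856 arm:

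- Head each dose column with the number of subjects ever at that level and the total subject-days there, from the SAP 13 days-at-dose variables.
- Count subjects once per PT within each level, with subjects ever at that level as denominator.
- Add onsets per 100 subject-days, at least for any AE and for AEs in at least 5% of subjects.
- Show onsets in the window of up to 9 days after the last dose (SAP 16.1) separately, or leave them out of the rates, so that numerator and denominator match. No dose is being taken then, and the SAP assigns none.
- Footnote that the table is descriptive, and that dose is not randomized and is confounded with time on treatment and tolerability.

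In SAP 6.7, name this table and the dose-at-discontinuation summaries in 16.1.2 and 16.1.3 as exceptions.

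The cost is SAP wording and minor programming. The downsides are sparse cells with about 24 active subjects (the 5% threshold is 24 × 0.05 = 1.2, so 2 subjects meet it) and rates that assume a constant hazard within each level.

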16.1.1.1. Severity

Severity is classed as mild/ moderate/ severe (increasing severity). AEs with a missing severity will be summarized as missing severity. If a subject reports an AE more than once within the same SOC/ PT, the AE with the worst severity will be used in the corresponding severity summaries. For this summary, AEs will be presented by SOC and PT for DB period, OL extension period.

16.1.1.2. Relationship to Study Medication

Relationship, as indicated by the investigator, is classed as “not related”/ “possible”/ “probable”/ “definite” (increasing strength of relationship). A dichotomous approach will be utilized for the safety output: a “related” AE is defined as an AE with a relationship to the study medication of “possible”, “probable” or “definite”. A “not related” AE is defined as an AE with a relationship to the study medication of “not related”. AEs with a missing relationship to the study medication will be regarded as “related” to the study medication. If a subject reports the same AE more than once within the same SOC/ PT, the AE with the strongest relationship to study medication will be used in the corresponding relationship summaries. For this summary, AEs will be presented by SOC and PT for DB period, OL extension period.

16.1.2. AEs LEADING TO DISCONTINUATION OF STUDY MEDICATION

AEs leading to permanent discontinuation of study medication are AEs for which “Drug Withdrawn” is selected for “Action Taken with Study Treatment” on the AE CRF page. A summary of AEs leading to discontinuation of study medication by SOC and PT will be presented for DB period and OL extension period, including dose at time of treatment discontinuation. A listing of AEs leading to discontinuation of study medication will be presented for DB period and OL extension period.

16.1.3. AEs LEADING TO DISCONTINUATION FROM THE STUDY

AEs leading to discontinuation from the study are AEs with “Caused Study Discontinuation” = “Yes” on the AE CRF page. A summary of AEs leading to discontinuation from the study by SOC and PT will be presented for DB period and OL extension period, including dose at time of early discontinuation. A listing of AEs leading to discontinuation from the study will be presented for DB period and OL extension period.

Document:

\

Author:

Version Number:

Final 1.0

Version Date:

24FEB2020

Template No: CS_TP_BS016 Revision 4
Effective Date: 01Apr2016

Reference: CS_WI_BS005

16.1.4. SERIOUS ADVERSE EVENTS

SAEs are those AEs recorded as “Serious” on the AE CRF page. Summaries of serious AEs and non-serious AEs by SOC and PT will be prepared for DB period and OL extension period. A listing of SAEs will be presented for DB period and OL extension period.

16.1.5. ADVERSE EVENTS LEADING TO DEATH

AEs leading to death are those AEs which are recorded as having an outcome of “Fatal” on the AE CRF page. A summary of AEs leading to death by SOC and PT will be prepared for DB period and OL extension period. A listing of deaths will be presented for DB period and OL extension period.

16.1.6. ADVERSE EVENTS BY SUBGROUP

As stated above, overall incidence summaries will be presented by the subgroups of race, sex, age, prior number of hospitalizations for PDP, the duration of PDP, and MMSE. The same subgroup factors will also apply to the by-subgroup summaries for the following events:

- All AEs, by SOC and PT

In addition, all AEs (by SOC and PT) will be summarized by the baseline BMI (kg/m^2) category:

- o Underweight: <18.5
- o Normal: 18.5 to <25.0
- o Overweight: 25.0 to <30.0
- o Obese: ≥ 30.0

16.2. LABORATORY EVALUATIONS

Laboratory data to be reported for this study include hematology, serum chemistry (including lipid panel and thyroid panel), urinalysis, coagulation, urine drug screening, Glycosylated haemoglobin (HbA1c), serum follicle stimulating hormone (FSH), prolactin, breath alcohol test and serum pregnancy test (only listed). A list of laboratory assessments to be included in the outputs is included in Section 21/ Appendix II of the CSP.

Presentations will use international system of units (SI).

Quantitative laboratory measurements reported as “ $< X$ ”, i.e. below the lower limit of quantification (BLQ), or “ $> X$ ”, i.e. above the upper limit of quantification (ULQ), will be converted to X for the purpose of quantitative summaries, but will be presented as recorded, i.e. as “ $< X$ ” or “ $> X$ ” in listings.

The following summaries will be provided for laboratory data for DB and OL period:

- By visit summary of observed values and changes from baseline for continuous data in hematology, chemistry, and urinalysis. Prolactin results will be summarized separately by gender. Glucose and lipid panel results will be summarized separately by fasting status.

Document:

\

Author:

Version Number:

Final 1.0

Version Date:

24FEB2020

Template No: CS_TP_BS016 Revision 4
Effective Date: 01Apr2016

Reference: CS_WI_BS005

- By visit summary of the number and percentage of subjects in each outcome category for categorical data in urinalysis and urine drug screening (if applicable). For urine drug screening, the results will be reported as "Positive"/ "Negative".
- Shift in lab results (chemistry, hematology, urinalysis) from baseline to Week 6 in DB period, and from baseline to post-OL baseline visits in OL period according to the reference range criteria provided by the central laboratory.

For the OL extension period, both the DB baseline and the OL baseline will be used in the calculation of change from baseline values, and for shift from baseline.

All laboratory data will be provided in data listings for DB period and OL period, with the values outside the reference ranges and that meet potentially clinically significant (PCS) criteria shown in Appendix 4 flagged.

16.3. ECG EVALUATIONS

Results from the central ECG (Electrocardiogram) will be included in the reporting of this study.

The following ECG parameters will be reported for this study:

- PR Interval (msec)
- RR Interval (msec)
- QRS Interval (msec)
- QT Interval (msec)
- QTcF Interval (msec) [derived]
- QTcB Interval (msec) [derived]
- Heart rate (HR) (beats/min)
- ECG findings
- Overall assessment of ECG (investigator's judgment):
 - Normal
 - Abnormal, clinically Significant [CS]
 - Abnormal, not clinically significant [NCS]

The following summaries will be provided for ECG data for DB period and OL period:

- By visit summary of observed values and changes from baseline (for quantitative measurements)

Document:

\

Author:

Version Number:
Version Date:Final 1.0
24FEB2020Template No: CS_TP_BS016 Revision 4
Effective Date: 01Apr2016

Reference: CS_WI_BS005

- By visit summary of ECG overall assessment results
- Shift in ECG overall assessments from baseline to Week 6 for DB period, and from baseline to post-OL baseline visits for OL period

Number and percentage of subjects with QTc levels in each of the QTc categories will be presented. For the OL extension period, both the DB baseline and the OL baseline will be used in the calculation of change from baseline values, and for shift from baseline.

The number and percentage of subjects with QTc values in the following categories will be identified for DB period and OL period. The same criteria apply to both QTcF and QTcB.

- > 450 msec at any post-baseline time point (including unscheduled visits) not present at baseline
- > 480 msec at any post-baseline time point (including unscheduled visits) not present at baseline
- > 500 msec at any post-baseline time point (including unscheduled visits) not present at baseline
- ≥ 30 msec and <60 msec increase from baseline for at least one post-baseline measurement (including unscheduled visits)
- ≥ 60 msec increase from baseline for at least one post-baseline measurement (including unscheduled visits)

All ECG parameters, overall interpretation, and findings will be provided in data listings.

16.3.1. ECG SPECIFIC DERIVATIONS

The following three measures are provided by the ECG vendor and those provided values will be analyzed. If one of these values is missing and derivation in the course of analysis is needed, the following derivations will be used:

- Bazett's Correction of QT interval (msec)
 - o $QTcB$ (msec) = $\frac{QT \text{ (ms)}}{\sqrt{RR \text{ (ms)}/1000}}$
- Fridericia's Correction of QT interval (msec)
 - o $QTcF$ (msec) = $\frac{QT \text{ (ms)}}{\sqrt[3]{RR \text{ (ms)}/1000}}$

Document:

\

Author:

Version Number:
Version Date:Final 1.0
24FEB2020Template No: CS_TP_BS016 Revision 4
Effective Date: 01Apr2016

Reference: CS_WI_BS005

- RR Interval – If RR Interval is not available it will be derived from HR as follows, for the derivation of the QTc corrections

$$\textcircled{o} \quad RR \text{ (msec)} = 1000 * \frac{60}{HR \text{ (bpm)}}$$

16.4. VITAL SIGNS

The following vital signs measurements will be reported for this study:

- Supine Systolic Blood Pressure (mmHg)
- Standing Systolic Blood Pressure (mmHg)
- Supine Diastolic Blood Pressure (mmHg)
- Standing Diastolic Blood Pressure (mmHg)
- Supine Pulse Rate (beats/min)
- Standing Pulse Rate (beats/min)
- Respiratory Rate (breaths/min)
- Temperature (C)
- Weight (kg)
- BMI (kg/m²)

The following summaries will be provided for vital signs data:

- Observed value and change from baseline by visit including the follow-up visit for DB period and OL period. For the OL extension period, both the DB baseline and the OL baseline will be used in the calculation of change from baseline values
- BMI Categories will be described by visit for DB period and OL period.

All vital signs data will be provided in a data listing for DB period and OL period, including flagging of PCS results.

PCS Criteria

Parameter Name	PCS Low	PCS High
----------------	---------	----------

Document:

\

Author:

Version Number:

Final 1.0

Version Date:

24FEB2020

Template No: CS_TP_BS016 Revision 4
Effective Date: 01Apr2016

Reference: CS_WI_BS005

Systolic Blood Pressure (mmHg) Standing and Supine	Value \leq 90 and \geq 20 decrease from baseline	Value \geq 180 and \geq 20 increase from baseline
Diastolic Blood Pressure (mmHg) Standing and Supine	Value \leq 50 and \geq 15 decrease from baseline	Value \geq 105 and \geq 15 increase from baseline
Pulse Rate (beats/min) Standing and Supine	Value \leq 50 and \geq 15 decrease from baseline	Value \geq 120 and \geq 15 increase from baseline
Weight (kg)	\geq 7% decrease from baseline	\geq 7% increase from baseline
Temperature (°C)	Value \leq 35°C	Value \geq 38.3°C
Respiratory (breaths/min)	Value \leq 11 and \geq 10 decrease from baseline	Value \geq 25 and \geq 10 increase from baseline

